Research question and objectives	What is the estimated risk of SCD among IBS-C patients prescribed linaclotide? What are the risk factors associated to SCD in patients with IBS-C? Specifically, linaclotide prescription.
Country(-ies) of study	United Kingdom, Sweden, Spain
Author	[REDACTED]

Marketing authorisation holder(s) (MAH)

Marketing authorisation holder(s)	AbbVie Deutschland GmbH & Co. KG [name] Germany
MAH contact person	[REDACTED] Pharmacovigilance & Patient Safety [REDACTED] Tel: [REDACTED]

2 LIST OF ABBREVIATIONS

5-HT4	5-Hydroxytryptamine 4
AE	Adverse event
AEMPS	Agencia Española del Medicamento y Productos Sanitarios
AIC	Akaike's Information Criterion
AP-DRG	All patients – diagnostic-related groups
ATC	Anatomical therapeutic chemicals
BIFAP	Base de datos para la investigación Farmacoepidemiológica en Atención Primaria
CD-ROM	Compact disk read-only memory
CI	Confidence interval
CKD	Chronic kidney disease
CPRD	Clinical Practice Research Datalink
DUS	Drug utilisation study
DVD	Digital versatile disk
EMA	European Medicines Agency
EMIS	Egton Medical Information System
EMR	Electronic medical records
ENCePP	European Network of Centres for Pharmacoepidemiology and Pharmacovigilance
EU	European Union
GP	General practitioner
GPP	Good Pharmacoepidemiology Practices
GPRD	General Practice Research Database
HES	Hospital Episode Statistics
IACS	Instituto Aragonés de Ciencias de la Salud
IBS	Irritable bowel syndrome
IBS-C	IBS predominately with constipation
IBS-D	IBS predominately with diarrhoea
IBS-M	IBS predominately with mixed bowel habits
ICD-10	International Classification of Diseases and Related Health Problems (10th revision)

ICD-9	International Classification of Diseases and Related Health Problems (Ninth Revision)
ICD-9-CM	International Classification of Diseases and Related Health Problems (Ninth Revision) Clinical Modification
ICH	International Conference on Harmonisation
ICMJE	International Committee of Medical Journal Editors
ISPE	International Society for Pharmacoepidemiology
ISPOR	International Society for Pharmacoeconomics and Outcomes Research
MAH	Marketing authorisation holder
MAOI	Monoamine oxidase inhibitors
MedDRA	Medical Dictionary for Regulatory Activities
MHRA	Medicines and Health Care Products Regulatory Agency
NEC	Necrotizing enterocolitis
NHS	National Health Service
NNH	Number needed to harm
NOS	Not otherwise specified (or unspecified)
NSAIDS	Non-steroidal anti-inflammatory drugs
O/E	On examination
OPCS	Operating procedure code supplement
OR	Odds ratio
PASS	Post-authorisation safety study
PCP	Primary care physician
PROTECT	Pharmacoepidemiological Research on Outcomes of Therapeutics by a European Consortium
PSUR	Periodic Safety Update Report
QPPV	Qualified person for Pharmacovigilance
R&D	Research & Development
RMP	Risk management plan
SCD	Severe complications of diarrhoea
SIDIAP	Information System for the Development of Research in Primary Care
SNOMED	Systematized Nomenclature of Medicine Clinical Terms

SNRI	Serotonin-norepinephrine reuptake inhibitor
SSRI	Selective serotonin reuptake inhibitors
STROBE	Strengthening the reporting of observational studies in epidemiology
TBD	To be determined
TCA	Tricyclic antidepressants
THIN	The Health Information Network
UK	United Kingdom
US	United States
UTS	Up to standard
WHO	World Health Organization

4 ABSTRACT

4.1 TITLE

Linaclotide Safety Study for the Assessment of Diarrhoea-Complications and Associated Risk Factors in Selected European Populations with IBS-C.

4.2 RATIONALE AND BACKGROUND

Irritable bowel syndrome (IBS) is a chronic, relapsing gastrointestinal condition characterised by abdominal pain, bloating, and changes in bowel habits. Prevalence estimations vary with the diagnostic criteria used, and in the United Kingdom (UK) were estimated between 9.5% and 22%. IBS can be classified according to Rome III criteria on the basis of the stool's characteristics: IBS predominantly with diarrhoea (IBS-D); IBS predominantly with constipation (IBS-C); and IBS with mixed bowel habits (IBS-M). Approximately one-third of IBS patients have each type of the disease.

The commercialisation of linaclotide (Constella[®]), a guanylate cyclase-C receptor agonist with visceral analgesic and secretory activities, was approved as the first medicine authorised for the symptomatic treatment of moderate-to-severe IBS-C in adults in the European Union (EU).

Therefore, this study is planned to assess the safety of linaclotide in terms of the risk of severe complications of diarrhoea (SCD) during treatment and other risk factors among patients with IBS-C.

4.3 RESEARCH QUESTION AND OBJECTIVES

The specific research questions and objectives for this study are to:

- Estimate the risk (case-control odds ratio [OR]) of SCD (case) among patients with IBS-C (source population) who received linaclotide prescriptions vs those who did not, controlling for other potential SCD risk factors (socio-demographics, comorbidities [up to 15], co-medications [up to 15] and other potential variables of interest [up to 10])
- Investigate potential risk factors associated to SCD in patients with IBS-C
- Describe the crude incidence of diarrhoea among patients with IBS-C

If allowed by the results of the cases and controls validation as discussed below, two additional objectives will be addressed:

- Describe the crude incidence of SCD among patients with IBS-C (source population) prescribed linaclotide (first-time users)

- Describe the crude incidence of SCD among patients with IBS-C (source population) prescribed linaclotide (first-time users) who are at increased risk of SCD:
 - Patients ≥ 65 years
 - Patients with hypertension, diabetes, or cardiovascular disease diagnostic codes

4.4 STUDY DESIGN

4.5 RETROSPECTIVE CASE-CONTROL NESTED IN A COHORT OF PATIENTS WITH IBS-C (CASES WILL BE PATIENTS SUFFERING FROM SCD) POPULATION

This study will use observational data from three different countries: the UK, Sweden, and Spain. The study population will be a cohort of IBS-C patients. Patients with less than 12 months of computerised records prior to IBS-C cohort entry date or no follow-up time will not be included.

4.6 VARIABLES

The outcomes of interest are severe complications of diarrhoea including dehydration that requires intravenous rehydration, dehydration that requires oral rehydration with solutions of electrolytes, electrolyte imbalance (potassium and sodium), oliguria, anuria, new onset-thromboembolism, new-onset orthostatic hypotension, new-onset syncope, new-onset dizziness, new-onset vertigo, acute renal failure, hypovolemic shock, hospitalisation due to diarrhoea, stupor, coma, or death.

All variables will be identified using diagnostic and procedure codes from general practitioner (GP) electronic medical records. IBS type and safety outcomes will be validated through a questionnaire to physicians treating the cases and controls included in the study.

4.7 DATA SOURCES

The feasibility of conducting the utilisation and safety study has been assessed in the countries of interest, and the most suitable databases identified are as follows:

- In the UK, the Clinical Practice Research Datalink (CPRD) contains information recorded by GPs as part of their routine clinical practice. Currently, CPRD offers two databases – CPRD GOLD and CPRD Aurum. CPRD Aurum contains data contributed by practices using Egton Medical Information System (EMIS), while CPRD GOLD holds data from In Practice Systems Limited Vision. As of March 2024, CPRD Aurum covered more than 24% of the UK population and CPRD GOLD covered approximately 4.4% of the UK population. Core data in both databases include information on socio-demographic characteristics, diagnoses, symptoms, referrals, tests ordered, some test results, prescriptions issued, and additional clinical information. Prescriptions as prescribed by the primary care physician (PCP) or GP have fields for strength and dose. Medical data in CPRD Aurum are coded using a mixture of Read, Systematized Nomenclature of Medicine Clinical Terms (SNOMED), and local EMIS codes; medical data in CPRD GOLD are coded using the Read coding system only. When linked to secondary care data from the Hospital Episode Statistics (HES), hospitalisation reasons for admission are coded by the International Statistical Classification of Diseases and Related Health Problems, 10th revision (ICD-10); hospital tests and hospital procedures are coded by operating procedure code supplement (OPCS) codes.

There is a potential for overlap between the two CPRD databases, since several GP practices that previously contributed data to CPRD GOLD when using In Practice Systems Limited Vision software are now supported by EMIS software, and have agreed to contribute data to CPRD Aurum. Where this is the case, duplicates will be removed, and only data from CPRD Aurum will be retained.

GPs can be contacted by researchers to request details beyond what can be found in the computerised records or to confirm details of patient conditions and treatments. The latest version of the datasets as of the data application date will be used.

- For Spain, the Information System for the Development of Research in Primary Care (SIDIAP) is a primary care database that collects longitudinal data from electronic medical records (EMRs) from 274 primary care centres in Catalonia since 2006, representing approximately 12% of the Spanish population. Data from primary care, specialised care, hospitals, and pharmacies are available, as well as patient characteristics like gender and date of birth, GP-diagnosed conditions, GP prescriptions, prescription dosing and size, date of prescription and dispensation, laboratory test results, other procedures, specialist referrals and diagnosis, hospital referrals, hospital procedures and discharge diagnosis, death date, and pregnancy information. GP diagnoses are coded following the ICD-10 codes, and hospital admissions are classified following the International Statistical Classification of Diseases and Related Health Problems, Ninth Revision (ICD-9). Since 2018, SIDIAP no longer allows the possibility to contact physicians for extracting extended additional information on the patient through long questionnaires. However, there is the possibility of a text review of the primary care records. This text review can be used to validate cases of interest and it would be conducted by IDIAP's clinical researchers. For this study, it is recommended by the data custodians that a review of free-text in the patient's medical records is conducted to improve the validity of the actual study, in place of the previously planned validation strategy using questionnaires to GPs. This free-text review will be made after an anonymisation process of the clinical records and a natural language processing of the text.
- For Sweden, the National Patient Registry (NPR) and Prescribed Drug Register (PDR): Information on diagnoses will be obtained from the Swedish NPR, which covers all public inpatient care since 1987 and all outpatient visits since 2001. The medical data include main and up to 21 secondary diagnoses and up to 30 surgical procedures from public and private service providers (National Board of Health and Welfare (Sweden), 2012). Diagnoses are coded using ICD-10 codes and surgical procedures with the Nordic Classification of Surgical Procedures. Primary care is not yet covered in the NPR. At present, the NPR is updated once a year.
Information about treatment use will be obtained from the Swedish PDR. Its coverage is close to 100% of all prescribed medicines from both primary health care centres and outpatient specialists dispensed to the Swedish population, and information is available since July 2005 (Wettermark et al., 2007). The register contains data on the substance, brand name, formulation, and package, dispensed amount, dosage, expenditure, and reimbursement as well as date of dispensing. Dispensation of over-the-counter (OTC) medications is not included.

4.8 STUDY SIZE

The sample size expected by 2016 in the three countries (available for analysis two to six months later) was at least 200,000 patients with IBS-C (cohort). Based on projected post-authorisation usage data provided by Almirall [MAH of linaclotide at the time of development of this protocol] in the linaclotide risk management plan (RMP), it was expected that roughly 9,665 patients using linaclotide could be captured by the proposed databases in the UK, Spain, and Sweden over the first four years of commercialisation, assuming Almirall [MAH of linaclotide at the time of development of this protocol] sales forecasts were correct, or approximately 5% of all patients with IBS-C would have been exposed to linaclotide.

In the progress report for 2016, users of linaclotide included in each of the study database were reported to be below the targeted numbers. Following the recommendation of the PRAC rapporteur, the end of the data collection was then extended by one year until December 2017. In October 2022, the PRAC recommended to further extend the study period in the UK until at least March 2021 or later if possible (the most recent CPRD and HES data at the time of data extraction), and include the CPRD Aurum dataset (in addition to the CPRD GOLD dataset originally proposed) to increase the sample size in the

UK.

Using the latest available information, the sample size across the three countries is approximately 329,000 patients with IBS-C or potential IBS-C, with an exposure to linaclotide rate ranging from 1% to 4%. If the results of the validation of cases are satisfactory with positive predictive value of SCD algorithms in the UK and Spain $\geq 95\%$, information from the whole cohort will be used to estimate risk of developing SCD across the groups of patients with or without linaclotide exposure, under a cohort study design. If the positive predictive values are $< 95\%$, a case-control analysis will be performed. Assuming the percentage of patients exposed to linaclotide among controls is around 1%, a minimum of 401 case-control pairs would be required to detect an $OR \geq 4$ and 745 possible case-control pairs to detect an $OR \geq 3$ with 80% power, under a matched case-control study design. Within the total IBS-C cohort, it is expected to accrue approximately 11,800 algorithm-identified, potential SCD cases. The final number of case-control pairs to be included in the analyses will depend on the performance of SCD algorithms and case validation results and is expected to be sufficient to detect an $OR \geq 3$ at 80% power, given the number of potential SCD cases identified by the algorithms.

4.9 DATA ANALYSES

Country-specific analyses will be conducted, and the heterogeneity of the results will be tested. If heterogeneity is not confirmed, then a pooled analysis aggregating data for all three countries will be conducted and country effect will not be assessed.

Patient characteristics at cohort entry date will be described for the full cohort of patients with IBS-C, as well as incidence rate of diarrhoea.

If the results of the validation of cases are satisfactory positive predictive value of EMRs in the UK and Spain $\geq 95\%$ and negative predictive value $\geq 99\%$, then information from the whole cohort will be used to estimate incidence and incidence density rates for those groups of patients with IBS-C prescribed linaclotide and those who are potentially at increased risk of SCD and prescribed linaclotide. The crude incidence of diarrhoea and of severe complications of diarrhoea will be described by calculating the proportion of patients with IBS-C experiencing diarrhoea and SCD, respectively, and their associated 95% confidence intervals (CIs). Crude incidence density rates of SCD will be also calculated.

Additionally, the hazard ratios of SCD and the exposures of interest (mainly prescription of linaclotide) will be estimated using Cox proportional hazard models. ORs of SCD and the same exposures of interest will be estimated using data from cases and matched controls by applying conditional logistic regression analysis.

If the results of the validation of cases in the UK and Spain are not satisfactory (positive predictive value of our outcome algorithm in the UK and Spain $< 95\%$ or negative predictive value $< 99\%$), only the nested case-control study will be performed and ORs of SCD and the same exposures of interest will be estimated using data from cases and matched controls by applying conditional logistic regression analysis.

The goal is to assess SCD among patients who were treated with linaclotide, were ≥ 65 years old, and had history of hypertension, diabetes or cardiovascular disease diagnostic codes (i.e., SCD occurrence is the outcome variable [yes/no]. and the independent variables of main interest are whether the patient has a prescription for linaclotide, a prescription for laxatives, the patient is ≥ 65 years old, and the patient has hypertension, diabetes, or cardiovascular disease diagnostic codes, all of them at index date, or not, controlling for potential confounders).

Statistical analyses will be conducted using SAS[®] statistical software.

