In response to the MAH's proposal, in the preliminary assessment report for the PASS protocol amendment submission (3rd Oct 2022), PRAC requested the MAH to extend the UK observational period up to the most recent possible date in order to include all available data and to revise the data collection period in the milestones accordingly, without further postponement of the final report (Q3 2023). The MAH contacted CPRD to confirm next steps for data extraction and validation study rerun. CPRD required that the MAH submits a new protocol to the CPRD review committee before requesting the new datasets and re-running the validation study. This is due to the change of dataset from CPRD GOLD to CPRD GOLD and CPRD Aurum, and the change of the observational period. The MAH submitted a new protocol to CPRD in April 2023 and expected to receive approval and the new datasets in Q3 2023. However, the actual process from application submission to data access took almost 12 months and the final data cut was eventually delivered in March 2024. The identification of new potential SCD cases as well as the initiation of validation activities have been completed in Q2 2024.

The validation of the diagnosis and SCD cases ended in Q2 2020 in Spain and expected to end in Q3 2024 in the UK. There is no validation study in Sweden. This study period is expected to allow for sufficient follow-up (long-term safety assessment) for those enrolled during the first period after linaclotide launch and for any subpopulations of interest (those with increased risk of SCD) to have the opportunity to accrue a sizable number of subjects for descriptive purposes. Please refer to Section 9.5 *Study Size* and Section 9.7 *Data Analysis* below.

[figure not shown]
The IBS-C cohort entry date for each cohort member will be defined as the date IBS-C criteria are first fulfilled or 01 February 2013 in Sweden, 13 May 2013 in the UK, and 01 September 2014 in Spain (linaclotide launch dates), whichever is the latest.

The follow-up period for each study subject in the IBS-C cohort will be from the cohort entry date to the earliest of the following (end of follow-up date; one day is the minimum follow-up (Figure 1):

- End of the study period
- Disenrollment from the database (date of transfer out of the practice or the PCP or Sweden)
- Date of last data collection for the practice
- Death
- Index date

The baseline period is the ≥ 12 -month period before IBS-C cohort entry date.

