9.5.2 NESTED CASE CONTROL SIZE

Table 3 illustrates a range of sample sizes required to have 80% power to detect a certain OR for those patients exposed or unexposed to a certain risk factor for SCD from a matched case-control study, assuming a range of proportions for exposure of the controls to the risk factor of interest.

A case-control study (Table 3) of SCD cases nested in a cohort of patients with IBS-C (like the one previously mentioned with 200,000 subjects) would require, for example, a total of 94 case-control pairs (equivalent to an incidence of SCD = 0.05%) with the necessary data for the analysis to have at least 80% power to detect an OR = 4 (or larger), associating SCD with a risk factor present in 5% of controls (in bold and grey background in Table 3).

Table 3. Sample Sizes (Case-Control Pairs) of Patients with IBS-C and Severe Complications of Diarrhoea (SCD) to Identify Increased Case-Control OR (Rate Ratio Estimate) for Risk Factors of Interest*

Percentage exposed among controls	OR=1.5	OR=2	OR=3	OR=4	OR=6	OR=8
0.1%	77656	22791	7252	3868	1831	1147
0.5%	15625	4595	1468	786	375	237
1.0%	7872	2321	745	401	193	123
2.0%	3996	1184	384	209	103	67
3.0%	2705	806	264	145	72	48
4.0%	2060	616	204	113	57	38
5.0%	1674	503	168	94	48	33
6.0%	1417	428	144	81	42	29
7.0%	1233	374	127	72	38	27
8.0%	1096	334	114	65	35	25
9.0%	990	303	105	60	33	23

* Significance level is two sided α 0.05 and power is $1 - \beta$ 80%, 1:1 number of cases (IBS C patients with severe complications of diarrhoea) to number of controls (IBS C patients without severe complications of diarrhoea) matched by number of years of active history in the CPRD (± 1 years), IBS C prevalent or incident status, and region. A higher number of matched controls per case would increase statistical efficiency (Pang D, 1999).

Abbreviations: OR odds ratio

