9.7 DATA ANALYSIS

Country-specific analyses will be conducted, and the heterogeneity of the results will be tested. If heterogeneity is not confirmed, then a pooled analysis will be conducted, and country effect will not be assessed.

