The CPRD provides a large, diverse, and representative sample of UK people using primary care services, which allows for generalizability of the study findings to the broader UK population. The General Practice Research Database (GPRD), predecessor to CPRD, has been widely used for observational studies, with over 890 studies published to date in peer-reviewed journals. The SIDIAP database includes information for 90% of the population in Catalonia, a region in northeast Spain, and resembling the data collected by the UK databases. One limitation is that date of prescription is only available for the first prescription and, thereafter, only an approximate date of dispensation is available. For Sweden, the NPR and PDR cover the entire Swedish population and have been previously used in observational studies including drug utilisation ones. However, no primary care data will be available, so diagnoses will be those determined by a specialist, which are expected to be required for the variables of interest for this study. The PDR is not complete with regard to drugs used in nursing homes.

According to the National Board of Health and Welfare, about 1% of people aged 65–79 years live in nursing homes, and about 20% of people aged 80 or more years live in nursing homes in Sweden [Socialstyrelsen]. This may be reflected in potential lower numbers of elderly patient using linacotide identified in Sweden.

The validity of research findings based on CPRD data and data from the other databases depends on the quality and completeness of the data recorded. We are only able to identify comorbidities for which the patient has consulted their GP. Referrals are not always uniformly coded and may appear as free-hand text or letters within the database.

Interval censoring might have an impact on the precision of the results.

Additionally, the proposed linked data sources (i.e., HES OP, HES AE and HES APC) have different linkage coverage periods. In particular, HES OP and HES AE linkage periods are considerably shorter than that of HES APC. This might increase the risk of SCD cases being underestimated. Finally, potential SCD are not classified by severity.

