SIDIAP is a primary care database launched in 2010. It is similar to CPRD or THIN in the UK and has been collecting longitudinal data from EMRs from 274 primary care centres in Catalonia since 2006. Catalonia is a region with a total of 5.8 million patients who represent approximately 12% of the Spanish population (4% of the Spanish population in SIDIAP-Q with higher-quality indicators). Data are updated once a year, and there are several scientific publications using this data source and reporting validation study results. The date of the latest available data is December 2013, and 2014 data will be made available by May-June 2015.

Data from primary care, specialised care, hospitals, and pharmacies are available, as well as patient characteristics such as gender and date of birth, GP-diagnosed conditions, GP prescriptions, prescription dosing and size, date of prescription and dispensation, laboratory test results, other procedures, specialist referrals and diagnosis, hospital referrals, hospital procedures and discharge diagnosis, death rate, and pregnancy information. GP diagnoses are coded following the ICD-10 codes, and hospital admissions following the ICD-9.

SIDIAP does not transfer data to private entities, but it can carry out quality investigation projects (Bolívar et al., 2012) and submit results upon their completion, which will be agreed upon with the funding body in the design stage of the study. It also allows physicians to be contacted using short questionnaires (currently a group that includes 10% of the total) to extract additional information on the patient through a questionnaire. Since 2018, SIDIAP no longer allows the possibility to contact physicians for extracting extended additional information on the patient through long questionnaires. However, there is the possibility of a text review of the primary care records. This free-text review is made after an anonymisation process of the clinical records and a natural language processing of the text.

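### Pooling of the three countries hangs on a heterogeneity test that cannot establish homogeneity at the sized pair numbers, with no validated UK+Spain estimate beside the pooled one

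*Protocol*

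**What the plan says.** Protocol Section 4.9 plans country-specific analyses and a test of heterogeneity. Where the test does not confirm it, a "pooled analysis aggregating data for all three countries will be conducted and country effect will not be assessed". Section 9.7 repeats the rule: "If heterogeneity is not confirmed, then a pooled analysis will be conducted, and country effect will not be assessed". Neither names the test or its threshold.

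Sections 4.9 and 9.7.1 allow the cohort analysis of SCD only if the positive predictive value is at least 95% and the negative predictive value at least 99%, judged in the UK and Spain. On Sweden, Section 9.2.1.4 says: "There is no validation study in Sweden". Section 9.2.1.2 defines some cases by serum potassium and sodium and notes that the Swedish register holds no laboratory results. Section 9.9 adds: "However, no primary care data will be available, so diagnoses will be those determined by a specialist".

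On access to Spanish data, Annex 3 (Proposed Data Source: SIDIAP) says: "SIDIAP does not transfer data to private entities". It adds that SIDIAP can run projects and submit results. Section 9.6 says that patient records will be collected from SIDIAP, and also that SIDIAP manages the Spanish data.

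**The concern.** The rule turns a failure to detect a difference into permission to pool and to stop looking at country. That is safe only if the test would probably detect a difference that matters.

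Here a difference is plausible on the protocol's own account. Swedish cases come from specialist and hospital diagnoses, without laboratory values and without validation. UK cases and Spanish cases draw on primary care records and are validated. If outcome misclassification differs by source, the country odds ratios can differ even when the drug effect is the same.

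At stake is a combined estimate that rests partly on an unvalidated, differently measured outcome, with no combined estimate from the two validated countries planned beside it.

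**Working it through.** **Inputs.** Section 4.8: 1% of controls exposed; 401 pairs for OR 4 and 745 for OR 3; about 11,800 algorithm-identified potential cases; exposure 1% to 4% across countries. Section 9.5.2: two-sided 0.05, 80% power, 1:1. Section 9.2.1.3: up to four controls per case. *Assumed, because the protocol does not state them:* Cochran's Q on 2 degrees of freedom at 0.05, the true country odds ratios, and the split of cases between countries.

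**Step 1: reproduce the plan's figures.** Matched-pair formula with P = OR/(1+OR), discordant pairs m = [z(α/2)/2 + z(β)√(P(1−P))]²/(P−0.5)², p1 = p0·OR/(1+p0(OR−1)), and pairs = m/[p1(1−p0)+p0(1−p1)].

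- OR 3: m = (0.980 + 0.8416×0.4330)²/0.0625 = 28.9; p1 = 0.0294; discordance rate 0.0388; pairs = 744.9. The plan says 745.
- OR 4: m = (0.980 + 0.8416×0.4)²/0.09 = 19.3; p1 = 0.0388; discordance rate 0.0481; pairs = 400.8. The plan says 401.

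So the sized study rests on about 29 or 19 exposure-discordant pairs in total. Split equally at 745 pairs, that is 28.9/3 = 9.6 per country.

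**Step 2: power of Q with few discordant pairs.** Simulation of 100,000 sets of binomial discordant pairs, with a 0.5 correction:

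| Discordant pairs per country | ORs 1/2/4 | ORs 1.5/3/6 |
|---|---|---|
| 10 | 10% | 6% |
| 29 | 52% | 42% |

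**Step 3: power by total pairs** (1:1, 1% exposure, equal split). The variance of each log OR is 1/a + 1/b, where a = n·p1(1−p0) and b = n·p0(1−p1) for n pairs per country. Power comes from the noncentral chi-square:

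| True ORs | 401 | 745 | 5,900 | 11,800 |
|---|---|---|---|---|
| 1/2/4 | 11% | 18% | 87% | 99% |
| 3/3/1.5 | 7% | 9% | 41% | 71% |
| 3/3/2 | 6% | 6% | 17% | 31% |
| 2/2/1.5 | 5% | 6% | 10% | 16% |

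The large-sample formula is optimistic at the two smaller sizes. Simulating whole pairs for ORs 1/2/4 gives under 1% at 401 pairs and about 6% at 745. The two methods agree closely at 5,900 (88% simulated) and 11,800 (over 99%). At 2,000 pairs they give 41% by formula and 37% by simulation.

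**Step 4: sensitivity.** The formula was repeated over three splits (equal; UK/Spain/Sweden 61/12/27; 28/25/47, the last being the Section 9.5 forecast for exposed patients), exposure of 1% throughout or 1% to 4% by country, and 1:1 or 1:4 matching:

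- ORs 3/3/1.5: 9–37% at 745 pairs, 65–100% at 11,800.
- ORs 3/3/2: 6–16% and 28–99%.
- ORs 2/2/1.5: 6–9% and 15–74%.

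**The case against.** Four points on the other side have weight.

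1. *The study may be much larger than 745 pairs.* Section 4.8 expects about 11,800 potential cases, so a reader who infers that the test is powerless whatever happens would be wrong. If even half of them are usable, a spread of 1/2/4 would probably be detected. This stands. But Section 4.8 also makes the final count depend on algorithm performance and validation, and modest differences stay hard to detect at the base settings even with every potential case.

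2. *Country is not ignored and differences are not hidden.* A reader might infer both. Country-specific analyses are unconditional. Section 9.2.1.3 matches on years of history in the database, which implies that controls come from the case's own source; conditional logistic regression then removes the country main effect. This stands for the case-control odds ratio. Matching does not stop different exposure effects from being averaged. No country stratum is stated for the Cox and SCD incidence analyses, though these run only if the predictive-value criteria are met.

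3. *The SIDIAP rule does not make pooling impossible.* It blocks a patient-level dataset at a private analyst, not the combination of country estimates. Section 4.9 speaks of aggregating data, which suggests the former, but Section 9.7 omits the phrase. What remains is a tension in wording with Section 9.6.

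4. *Giving no overall figure when heterogeneity is confirmed is defensible.* One might call this an empty branch, since the sizing is for all three countries. But Section 7 calls the study descriptive without an a priori hypothesis, and declining to average effects shown to differ is a legitimate choice.

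The test and threshold may properly sit in the SAP. The logic of the gate is fixed in the protocol.

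**Conclusion.** The point holds in a limited form. Making pooling depend on unconfirmed heterogeneity is unsound, because at 401 to 745 pairs and 1% exposure the test would miss even ORs of 1/2/4 about nine times in ten or more (simulated, 1:1, equal split). With all 11,800 potential cases it would detect that pattern almost surely, but would still miss 3/3/2 about 69% of the time and 2/2/1.5 about 84% of the time under the same settings. These figures rest on an assumed test, alpha, set of country odds ratios and split; 1:4 matching or higher exposure raises them.

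The consequence is confined to the pooled result. A country-by-exposure difference, most plausibly between Sweden and the two validated sources, would be averaged into the pooled estimate, and any pooled Cox or SCD incidence analysis would have no country stratum. The documents do not support the stronger inferences that country differences go unreported, that the case-control odds ratio is confounded by country, or that Spanish data cannot contribute to a pooled result.

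**What to change.** - In Sections 4.9 and 9.7, report heterogeneity as description and remove it as the gate for pooling.
- Form the pooled estimate in two stages from the country log odds ratios or log hazard ratios. This works with the SIDIAP rule in Annex 3.
- Report a combined UK+Spain estimate next to any three-country estimate.
- Stratify any pooled Cox model by country, and give incidence by country.
- Reconcile Section 4.9, Section 9.6 and Annex 3 on whether patient-level Spanish records leave SIDIAP.

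The choice of fixed or random effects can be left to the SAP, since the between-country variance is poorly estimated from three countries.

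The cost is wording, a little more analysis of estimates that are already planned, and possibly a wider interval for the pooled figure. No new data are needed.
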